3.1.1.3 Process and fidelity measures

- Days from randomisation to treatment initiation.
- Physiotherapy (PKT and post-operative rehabilitation) and surgical CRFs to assess intervention fidelity including information on:
 - o Number of physiotherapy sessions offered and attended
 - Composition of physiotherapy

• Participant CRFs to assess intervention adherence, including information on number of physiotherapy sessions attended, at six, 12, 18 and 24 months postrandomisation.

3.1.2 Equality, Diversity, and Inclusion

It is important that we ensure that all potential participants have the same opportunity to take part. We have carefully addressed this in our choice of sites and in our recruitment and trial processes to ensure all eligible patients who present are informed about the trial. As part of baseline data capture, we will collect equality and diversity measures to assess if the trial population is representative of the population of interest. Specifically, we will collect data on age; disability; gender reassignment; marriage and civil partnership; pregnancy and maternity; ethnicity; religion or belief; sex; sexual orientation; socioeconomic status (based on postcode district).

We will monitor reasons for exclusion on CONSORT charts at monthly TMG meetings and address any potential issues as they arise.

We will support participants during their research journey, monitoring for any reasons that they may be finding it hard to engage in study processes. We will include costs for clinical follow-up at 12 and 18-months to ensure people have access to their healthcare teams and to help with outcome collection.

3.1.3 Safety

Adverse Events and Serious Adverse Events will be managed following GCP guidelines and Warwick SOPs. Details of this are given in section 4 of the protocol.

3.1.4 Health economics measures

A prospectively planned economic evaluation will be conducted from an NHS and personal social services perspective, according to the recommendations of the NICE reference case.(64) Bespoke resource utilisation questionnaires will be developed to meet the specific needs of the trial. Health service and social service contacts, made in connection with participant's treatments will be recorded as part of the resource utilisation questionnaires. Time lost from work (paid/unpaid), will also be recorded. A detailed Health Economic Analysis Plan (HEAP) will be developed.

3.2 Schedule of delivery of intervention and data collection

Table 2. Schedule of delivery of interventions and data collection

Visit/follow-up number	-1	1	2	3		4	5	6	7
Visit/follow-up	Screening	Baseline	Pre- intervention (to be collected within 4 weeks before intervention starts)	Intervention	Medical note review	6-month follow-up	12-month follow-up	18-month follow-up	24-month follow-up
Time after randomisation (±window)	-	0		Data within 4 weeks of completion of allocated treatment	As required from randomisation to 24 months	6 months (-6w/+3m)	12 months (±3m)	18 months (±3m)	24 months (-3/+6m)
Check eligibility \$	✓								
Invitation to study \$	✓								
Informed consent \$		✓							
Medical history \$		✓							
Inclusion/exclusion criteria \$		√							
Randomisation \$		✓							
Intervention (PKT/ surgery & post op physio) ^{\$}				√					
Adverse events \$#					✓	✓	✓	✓	✓
Patellar dislocations and further surgery \$#					√	√	√	√	✓
Rehabilitation attendance \$#					√	√	√	√	✓
KOOS4 #			✓						
KOOS #		✓				✓	✓	✓	✓
NPI#		✓				✓	✓	✓	✓

EQ-5D-5L #	✓	✓		✓	✓	✓	✓
Work or education status #	√			√	√	√	√
PROMIS satisfaction with social roles#	√			√	√	√	√
Satisfaction with treatment #				√	✓	~	~
Social activities #				✓	✓	✓	✓
PGIC#				✓	✓	✓	✓
Problems and complications #				√	~	√	√
Health resource use #				✓	✓	✓	✓
Painkiller use #				✓	✓	✓	✓

^{\$} site completed

[#] participant completed

4. ADVERSE EVENT MANAGEMENT

4.1 Definitions

4.1.1 Adverse Events

An Adverse Event (AE) in this study will be defined as any untoward medical occurrence in a participant taking part in health care research, which does not necessarily have a causal relationship with the research. However, for the purposes of this trial, and to avoid unnecessary recording of events, we will only collect AEs or Serious Adverse events (SAEs) related to their treated knee and to the treatment they receive in the trial (or any treatment for their treated knee) or related to trial processes.

4.1.2 Recording adverse events

AEs related to the surgical procedure including the surgery, anaesthetic, post-operative care and rehabilitation, any component of the Personalised Knee Therapy package, or any knee treatment in the AE reporting period will be recorded on the appropriate CRF for return to the trial central office and reported to the relevant oversight committees.

AEs related to the treated knee, treatment received in the trial (or any treatment for their treated knee) or related to trial processes will be collected from the point of randomisation onwards, up to 24-months.

Some events which occur during treatment and recovery will be considered normal aspects of the therapy, anaesthetic and post-operative recovery process and will not need reporting as AEs or SAEs unless in the opinion of the clinical team, they are untoward, excessive, or outside of what might normally be expected for the procedure. These are normal events that occur frequently after physiotherapy or surgery and include:

- Nausea and/or vomiting after surgery.
- Drowsiness or headache after surgery.
- Temporary low blood pressure after surgery.
- Sore throat after surgery.
- Itching after surgery.

- Post-operative or post-intervention pain in the first six months (note that pain after six months will be collected as an outcome in the study, using the KOOS pain domain).
- Numbness on the lateral side of the surgical wound.
- Early wound oozing which spontaneously resolves.
- Swelling, within the confines of what is considered normal post-intervention swelling by the treating clinical team.
- Restriction of range of motion, within the confines of what is considered normal post-operatively by the treating clinical team.
- Bruising, unless this is considered abnormal by the treating clinical team.
- Post-intervention pain, muscle soreness or tiredness during or after physiotherapy
 (in-patient and out-patient) in either group.
- Ongoing instability symptoms.

All recorded AEs will be monitored for trends, see section 4.2 for responsibilities. An outcome of 'not yet resolved' is an acceptable final outcome for non-serious AEs at the end of a patient's participation in a trial.

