A 2017 systematic review (updated searches 2022) of non-operative care in the management of patellar dislocation comprising of assessment, strengthening exercise prescription (hip and knee), and orthotics, found wide variation in treatments and outcomes.(11) There were few data on recurrent dislocations, and even after first-time dislocations, there was only poor-quality data, mostly case series. Some studies highlighted persisting disability despite non-operative care, even with no further dislocations.(17) The evidence also highlighted that whilst there was an emphasis on quadriceps (thigh muscles) strengthening exercises, there was limited provision of other exercises and non-operative care strategies which may offer benefit including flexibility exercises, glutei recruitment (buttock muscle activity) programmes or orthoses (external devices or braces). Whilst there has been promise in other knee rehabilitation interventions for a tailored intervention programme, such as grading recovery by identifying patient goals related to return to work and sporting pursuits, this has only been piloted in this population in our feasibility study.(25, 32, 33)

Reviews of operative management consistently recommend medial patellofemoral ligament (MPFL) reconstruction(18, 34, 35), consistent with national guidelines described below. A tibial tubercle osteotomy may be added where patella alta (a high kneecap) is present.(18, 36, 37) Other operative procedures such as trochleoplasty or rotational osteotomy are occasionally required for complex anatomical deformity, but these are relatively rare (less than 10% of the recurrent dislocation population). People with these rare anatomical deformities are typically very difficult to treat with therapy alone, and surgery has a different recovery and complication profile to the procedures used for the majority of people with recurrent dislocation.(38)

Case series have reported good outcomes for MPFL reconstruction, alone or combined with tibial tubercle osteotomy, although functional outcome scores do not return fully to normal.(34, 36, 37, 39)

Reported complication rates of MPFL reconstruction are 3-7% (including: infections, deep vein thrombosis, pulmonary embolism, reoperation) with re-dislocation rates of 2-5%. Tibial tubercle osteotomy has a complication rate of around 5%, but subsequent removal of screws is common (30-50%).(40)

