 (frequently quadriceps complex) and recruitment (frequently glutei complex)
 exercises, flexibility (frequently hamstring complex, iliopsoas, gastrocnemius)
 exercises, and proprioceptive exercises
- Analgesia
- Activity advice with graduated exposure to activities which individuals identify as perceived threats for recurrent dislocation
- Non-weightbearing
- Patellar stabilising orthoses and braces
- Electrostimulation

IRAS ID: 321908

- Exercise/group gym classes
- Manual therapy
- Cognitive behavioural approaches

Exercises will be individually prescribed from a core template of exercises. The programme will be supervised by a physiotherapist, and then practised at home with a comprehensive home rehabilitation plan. This will be supported, and adherence promoted, with a treatment booklet providing guidance on exercises prescribed and general recovery advice, using paper, web based or MyRecovery patient App (https://www.msk.ai/patients) materials.

Phases of treatment: The PKT programme has three phases.(25) These are framed on functional progression, based on objective criteria with an early, middle, and later phase of treatment.

- Progression from early to middle phases required the person to have good range of motion and quadriceps strength with minimum pain.
- Progression from middle to later phase (return to sport and higher-level function)
 required the person to have good proximal muscle control with rotational stability
 on multi-directional activities.
- People who experienced instability symptoms or recurrent dislocation were required to return to an earlier phase.

Site training will be provided to all physiotherapists delivering the intervention to promote fidelity to the programme. This will occur prior to sites opening and where possible, in alignment with site initiation visits. Training will be delivered by the central trial team.

As with surgery, the time from randomisation to the start of the Personalised Knee Therapy intervention (first physiotherapy contact) will be recorded. Reporting of both interventions will conform to the TIDieR checklist.(50)

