3.1.1.2 Secondary Outcomes

- KOOS4 at baseline, pre-intervention, six, 12, and 24-months.
- The five individual KOOS domains (symptoms, pain, activities of daily living, sports, quality of life)(54, 58) at baseline, six, 12, 18, and 24-months post randomisation.
 The KOOS5 is a validated knee specific instrument developed to assess the patients' opinion about their knee and associated problems.
- NPI score(15) at baseline, six, 12, 18, and 24-months post-randomisation.
- Health utility (EQ-5D-5L)(59, 60) at baseline, pre-intervention, six, 12, 18, and 24-months post-randomisation. The EQ-5D-5L is a validated measure of health status consisting of five dimensions each with a five-level answer possibility. Each combination of answers can be converted into a health utility score. It has good test-retest reliability, is simple for participants to use, and gives a single preference-based index value for health status that can be used for broader cost-effectiveness comparative purposes.
- Work or education status (time off, change to status) at baseline, six, 12, 18, and 24months post randomisation.
- Satisfaction with social roles (PROMIS scale)(61) at baseline, six, 12, 18, and 24months post randomisation.

- Satisfaction with treatment(62) at six, 12, 18, and 24-months post-randomisation using a 5-point Likert scale.
- Patient global impression of change (PGIC) scale (single item)(63) at six, 12, 18, and
 24-months post-randomisation. This is a simple 7-point scale assessing perception of improvement.
- Patellar dislocations at baseline, six, 12, 18, and 24-months post-randomisation
- Adverse events including surgical complications at six, 12, 18, and 24-months post-randomisation (see section 4).
- Further knee surgery (either arm) at six, 12, 18, and 24-months post-randomisation.
- Resources used by interventions and assessed at six, 12, 18, and 24-months postrandomisation.

As there may be a differential wait for the intervention between arms, we will collect KOOS4 and EQ-5D-5L within four weeks before the start of intervention (both arms).

We will minimise missing data utilising experience from the feasibility trial, including paper and app-based solutions, telephone and text reminders, multiple contact details, clinical follow-up, and vouchers with the 18-month follow-up invitation.(25)

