4.1.3 Serious Adverse Events (SAEs)

A Serious Adverse Event (SAE) is an AE, as defined for this trial (see 4.1.1), that fulfils one or more of the following criteria:

- Results in death.
- Is immediately life-threatening.
- Requires hospitalisation or prolongation of existing hospitalisation.
- Results in persistent or significant disability or incapacity.
- Is a congenital abnormality or birth defect.
- Immediate intervention was required to prevent one of the above or is an important medical condition.

For the purposes of this trial, as with AEs, we will only collect SAEs related to the participant's treated knee, to the treatment they receive in the trial (or any treatment for their knee) or related to trial processes.

Further knee surgery only needs to be reported as an SAE if it results from a complication of the allocated trial treatment (such as infection). Persistent pain without new pathology or other event will not be considered an SAE as this will be recorded in outcome scores.

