4.1.7 Assessment of Expectedness

Where reported, SAEs will be assessed for having a possible causal relationship with the intervention or its associated procedures. Where a causal relationship is established an evaluation of expectedness will be made by the CI or their delegate, using the list below. The following are SAEs that are expected as a result of the intervention and its associated procedures:

Those related in general to surgery and anaesthetic:

- Injury to teeth, mouth, or throat during anaesthetic.
- Chest infection.
- Nerve or vessel injury due to local anaesthetic (i.e., local blocks or spinal anaesthetic).
- Spinal haematoma.
- Stroke or Cardiac Event.
- Death.

Those related to the operation itself or physiotherapy:

- Exacerbation/persistence of knee pain or instability beyond what is considered
 normal by the treating clinical team. As this outcome will be captured in Patient
 Reported Outcome Measures (PROMs) throughout the study, only medical or
 surgical interventions for persistent knee pain need to be reported.
- Restriction of range of motion, including need for manipulation under anaesthetic,
 arthroscopic or open procedures to relieve stiffness.
- Infection.
- Wound healing problems.
- Fracture, ligament or tendon damage or rupture.

- Revision surgery or other corrective surgery.
- Irritation from metalwork or surgery to remove metalwork.
- Thrombosis (deep vein thrombosis, pulmonary embolus, cerebral infarct).
- Damage to nerves or vessels.
- Persistent muscle soreness or muscle injury.
- Bruising.
- Swelling.
- Skin damage (for example, from bracing).
- Exercise-related fatigue.

Treatments of expected events listed above (such as surgery for infection or wound problems) are also expected events.

If the SAE is not listed above and is considered to have at least a possible causal relationship to the intervention, the event would therefore be classified as unexpected and will be reported to the REC within 15 days.

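### Re-dislocation of the study knee is a separate outcome, but the adverse-event rules neither exclude nor name it, so treatment failure can be mixed into the harm comparison

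*Protocol*

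**What the plan says.** **Two separate outcomes.** Protocol 3.1.1.2 lists "Patellar dislocations at baseline, six, 12, 18, and 24-months post-randomisation" and, as a different item, "Adverse events including surgical complications at six, 12, 18, and 24-months post-randomisation". Table 2 gives them different rows. Section 2.2.2 plans to quantify and draw inferences on both.

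**What is collected as an AE.** Section 4.1.2 collects "AEs related to the treated knee, treatment received in the trial (or any treatment for their treated knee) or related to trial processes", so a link to the knee alone is enough. Sections 4.1.1 and 4.1.5 join knee and treatment with 'and', so both links are needed (or a link to trial processes). Section 4.1.3 refers back to 4.1.1 but lists the links as alternatives.

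**What is exempt.** The 4.1.2 list of normal events includes "Ongoing instability symptoms" and does not mention dislocation. Section 4.1.3 removes two other kinds of treatment failure from serious-event reporting. Further knee surgery counts only if it results from a complication of the allocated treatment. For pain the rule is: "Persistent pain without new pathology or other event will not be considered an SAE as this will be recorded in outcome scores". Dislocation has no such rule.

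**What is expected.** Section 4.1.7 names worsening or persistence of knee pain or instability, but not dislocation. The residual rule opens "If the SAE is not listed above and is considered to have at least a possible causal relationship to the intervention" and classes such an event as unexpected, with a report to the ethics committee within 15 days.

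**The concern.** The AE outcome should show what each strategy costs the patient in harm. Re-dislocation is the event both strategies aim to prevent, and the review evidence in section 1.2.2 suggests it is less frequent after surgery. The same evidence has surgery producing more AEs. The two effects point in opposite directions, so one count that contains both can hide the harm of surgery behind its benefit.

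The monitoring committee reviews safety by allocation group (4.2), so a mixed count would reach it as well as the final report. Section 4.1.4 also lets the coordinating centre pick up AEs from specific CRF questions, and dislocations are asked about at every follow-up.

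**Working it through.** **1. Do the exempt and expected lists cover dislocation?** Section 1.1.1 describes instability as what is felt between dislocation episodes. Section 2.8.1.1 names the two as alternatives: "People who experienced instability symptoms or recurrent dislocation". On these uses, the exempt item does not cover a dislocation. Against that, 1.1.1 also adopts 'patellar instability' as the name of the whole condition. The lists are therefore open to two readings.

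**2. What enters under each AE wording?** With 'or' (4.1.2), every untoward re-dislocation of the study knee enters unless a site reads the exempt list as covering it. With 'and' (4.1.1, 4.1.5), only those judged treatment-related enter. Staff know the allocation (2.9), and the judgement is easily made differently after a ligament reconstruction and after physiotherapy. Neither wording keeps the two outcomes apart.

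**3. Size.** No stated figure is disputed. The sample size reproduces: 21 × √(1 − 0.5²) = 18.2; a difference of 8 at 90% power and two-sided 5% needs 110 per group; 110/0.8 rounds up to 138 per arm, 276 in total.

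Inputs, all from section 1.2.2:
- complications after MPFL reconstruction, c = 3-7% (3, 5 and 7% used)
- re-dislocation after surgery, d = 2-5% (2 and 5% used)
- dislocation RR 0.47, CI 0.32 to 0.71 (all three values used)
- AE RR 9.10

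Assumptions: complications and re-dislocation are independent, and the therapy (PKT) arm has AE risk c/9.10 and re-dislocation risk d/RR.

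Risk of any event: surgery 1 − (1 − c)(1 − d); PKT 1 − (1 − c/9.10)(1 − d/RR). Without re-dislocations the ratio is 9.10 throughout. With them, at 138 per arm:

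| c | d | RR | Surgery | PKT | Ratio |
|---|---|---|---|---|---|
| 3% | 5% | 0.32 | 7.85% (10.8) | 15.90% (21.9) | 0.49 |
| 3% | 5% | 0.47 | 7.85% (10.8) | 10.93% (15.1) | 0.72 |
| 7% | 2% | 0.47 | 8.86% (12.2) | 4.99% (6.9) | 1.77 |
| 7% | 2% | 0.71 | 8.86% (12.2) | 3.56% (4.9) | 2.49 |

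The first and last rows are the extremes of the 3 × 2 × 3 = 18 combinations. Six fall below 1.

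**4. Break-even.** With S the surgical any-event risk, the ratio equals 1 when PKT re-dislocation is (S − c/9.10)/(1 − c/9.10). This is 4.6% for c = 3%, d = 2% and 11.0% for c = 7%, d = 5%. The inputs above imply PKT rates from 0.02/0.71 = 2.8% to 0.05/0.32 = 15.6%.

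Setting the unknown PKT rate directly, with c = 3 or 7% and d = 2 or 5%, gives these ratios:
- 5%: 0.93-2.03
- 10%: 0.48-1.09
- 15%: 0.32-0.74
- 40%: 0.12-0.29

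**5. Screw removal.** Section 1.2.2 gives 30-50% screw removal after tibial tubercle osteotomy, and 2.8.1.2 gives patella alta in 30-50%. If every such patient had the osteotomy and each removal counted as an AE, the surgery arm would gain 0.3 × 0.3 = 9% to 0.5 × 0.5 = 25%.

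Take the lowest row of the table with 9% added. Surgery becomes 1 − 0.97 × 0.91 × 0.95 = 16.1% against 15.9%, a ratio of 1.02. If the PKT AE risk is instead scaled to keep 9.10, PKT is 16.7% and the ratio 0.97. Reversal then all but disappears. Dilution does not: with the PKT AE risk left at c/9.10, the ratio across the 18 combinations falls from 20.0-35.6 to 1.0-4.8.

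**The case against.** **Nothing says re-dislocations are counted as AEs.** The protocol lists them apart every time, the exempt list is illustrative, and the defining section (4.1.1) uses the narrower wording. This stands in part: a reader might infer that every re-dislocation is an AE, but that follows only from the wording of 4.1.2. Separate listing, however, does not stop a site recording the same event under both headings.

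**Unblinded causality judgement affects every AE in an open trial.** True, but few other events are also an efficacy outcome expected to differ between the arms.

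**Instability in 4.1.7 may cover dislocation, and over-reporting is cautious.** The first is arguable. The second is fair for the ethics committee, since only serious, possibly related events go there. Neither makes sites classify alike.

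**Tabulation belongs to the SAP.** Fair for the tables. The recording and expectedness rules are protocol text, and between-arm inference on AEs is a stated objective.

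**Re-dislocation may be a legitimate AE.** This stands. After a reconstruction it may be failure of the procedure, and the monitoring committee may want to see it. The remedy should not depend on removing it from recording.

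**A reader might infer that the harm comparison will reverse, perhaps heavily.** Assume 20-40% re-dislocation under PKT, with other AEs in 5% (surgery) and 1% (PKT). Surgery is then 1 − 0.95 × 0.98 = 6.9% to 1 − 0.95 × 0.95 = 9.8%, and PKT 1 − 0.99 × 0.80 = 20.8% to 1 − 0.99 × 0.60 = 40.6%, a ratio of 0.17-0.47. The documents do not support this. The PKT rates are not given, and against 2-5% after surgery they imply a dislocation RR of 0.02/0.40 = 0.05 to 0.05/0.20 = 0.25, outside the quoted interval of 0.32 to 0.71.

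**Conclusion.** The point holds as a defect in the recording rules, with a consequence for the AE outcome. Read as written, the protocol lets a study-knee re-dislocation enter the harm count, always or on an unblinded judgement depending on which section a site follows, and gives no single classification for it.

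On the protocol's own rates, counting re-dislocations moves the surgery-to-PKT AE ratio from 9.10 to about 0.5-2.5. Strong dilution of the surgical excess is the firm finding. Reversal is possible (6 of 18 combinations), not certain, and becomes unlikely if screw removals are counted as AEs.

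The size rests on an unstated PKT re-dislocation rate, on independence of the two events, and on risk ratios drawn mainly from first-time dislocation; the dislocation ratio also covers two to five years rather than 24 months. Dislocations while waiting for surgery would raise the surgical rate above 2-5%. The primary outcome is unaffected. The change is worth making because it is cheap.

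**What to change.** Reconcile 4.1.2, 4.1.3 and 4.1.7 (and the 'and'/'or' wording of 4.1.1 and 4.1.5) with the dislocation outcome. State one rule, identical in both arms, for how a study-knee re-dislocation is recorded and whether it is classed as expected. Make clear that injuries resulting from it, and any event meeting a seriousness criterion, remain reportable.

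In the reports, tabulate AEs and SAEs by arm excluding re-dislocation, show re-dislocations beside them, and give the total including them. The comparison can then be read whichever recording rule is adopted.

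Cost: a few sentences in the protocol and one extra table. No new data are needed, because Table 2 already collects dislocations separately. The downside is a smaller headline AE count, which the combined total offsets.
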